APPENDIX D: THE DEFINITIONS OF CYTOMEGALOVIRUS DISEASE

Cytomegalovirus Disease Definitions

The definitions of cytomegalovirus disease are provided in Ljungman et al.¹

Sources:

1 INTRODUCTION

The purpose of this Statistical Analysis Plan (SAP) is to provide a description of the statistical methods to be implemented for the analysis of data for Nobelpharma Co., Ltd. protocol NPC-21-2 (Version 5.0; 18 October 2021). The SAP will be finalized prior to database lock. Any deviations from the SAP after database lock will be documented in the final Clinical Study Report (CSR).

2 STUDY OVERVIEW

2.1 Study Objectives

2.1.1 Primary Objective

The primary objective is to assess the efficacy and safety of NPC-21 when administered prophylactically to cytomegalovirus (CMV) seronegative patients receiving a first kidney transplant from a CMV seropositive donor.

[figure not shown]
2.2 Study Design

2.2.1 Overview

This is a Phase 2, randomized, double-blind, placebo-controlled study of NPC-21 for kidney transplant recipients at high risk of CMV infection at approximately 25 clinical sites in the United States and Japan. Approximately 108 eligible patients will be randomized in a 4:1:4 ratio prior to first study drug administration to receive 6 mg/kg NPC-21, 12 mg/kg NPC-21, or placebo. Randomization will be stratified by region (United States or Japan).

Figure 1 displays a schematic of the study's design.

Figure 1. Study Schematic

*When the patient meets the primary endpoint, the patient move to the rescue phase

Adult CMV seronegative patients receiving a first kidney transplant from CMV seropositive donors will be enrolled in the study. Participation in the study will consist of a Screening Period (up to 14 days prior to first study drug administration), a 16-week Treatment Period, and a 12-week Observation Period. The total duration of the study (including Screening, Treatment Period, and Observation Period) will be approximately 30 weeks. After first study drug administration, patients who develop detectable CMV disease (CMV syndrome or tissue-invasive CMV disease) or CMV viremia (defined as the detection of ≥ 250 IU/mL in plasma measured by polymerase chain reaction [PCR] analysis in central laboratory or meets the local criteria for CMV viremia measured by PCR analysis or antigenemia testing) can enter the Rescue Phase of the study and be treated by anti-CMV agents per local standard of care until the patient is negative for CMV viremia, has recovered from CMV disease, or up to Week 28, whichever comes first. When this rescue therapy is completed, the Rescue Phase is terminated at least 4 Study Weeks after the last study drug administration and all Week 28 procedures will be performed as per Section 6.7 the Early Termination Visit and Withdrawal Procedures of the protocol.

The 16-week Treatment Period will include study drug administration on Day 1 and at Weeks 4, 8, and 12. The 16-week Treatment Period will begin as soon as practical post-transplant but no later than 7 days post-transplant.

Blood samples will be collected at Screening; prior to study drug administration on dosing days (Day 1 and at Weeks 4, 8, and 12); and at Weeks 1, 2, 3, 5, 6, 7, 9, 10, 11, 13, 14, 15, 16, 17, 18, 19, 20, 21, 22, 23, 24, 26, and 28 for CMV deoxyribonucleic acid (DNA) analysis utilizing PCR analysis or CMV antigenemia testing. The central laboratory will perform CMV PCR analysis, and the local laboratory will perform CMV PCR analysis or CMV antigenemia testing consistently throughout the study. Upon entering the Rescue Phase, a blood sample will be collected for CMV DNA analysis utilizing PCR analysis performed by the central laboratory.

Blood samples for anti-NPC-21 antibody testing will be collected prior to study drug administration on dosing days (Day 1 and at Weeks 4, 8, and 12) and at Weeks 16 and 28.

Blood samples that will be stored for screening for resistant strains analysis will be collected prior to study drug administration on Day 1 and at Weeks 16 and 28 and at the initiation of the Rescue Phase.

Blood samples for serum NPC-21 concentration measurements will be collected within 2 hours prior to study drug administration and at 2 hours (± 30 minutes) following the beginning of the infusion on dosing days (Day 1 and at Weeks 4, 8, and 12) and at Weeks 1, 2, 3, 6, 10, 14, 16, 20, 24, and 28 (Note: Sample collection time points at each visit may be updated based on each administration data).

The EuroQol 5 Dimensions 5 Levels questionnaire (EQ-5D-5L) will be performed prior to study drug administration on Day 1, at Weeks 16 and 28, and at the initiation of the Rescue Phase.

The safety of NPC-21 in CMV seronegative patients will be evaluated through physical examination findings, 12-lead electrocardiograms (ECGs), vital signs, changes in clinical laboratory assessments (blood biochemistry [including liver function tests and enzymes], hematology [including complete blood count with differential], coagulation, and urinalysis), and adverse event (AE) monitoring.

2.2.2 Randomization

At Screening, a unique patient identification number will be established for each patient who has provided written informed consent. This patient identification number will be used for patient identification throughout the study and in all study-related documentation. This will be a 5 digit hyphenated number of the following format: XYY-ZZ, where X is the country number (1 [US] or 2 [Japan]), YY is the sequential unique site identification number, and ZZ is a sequential unique number assigned to the patient at that site.

Each patient number will be assigned only once and will not be reassigned to another patient if a patient fails during Screening. Interactive Response Technology (IRT) will not allow repeat of numbers. This unique identifier will be used in all study documentation for that patient from first to last contact.

After informed consent and body weight are obtained, pre-Randomization will take place via the IRT system to 1 of 3 treatment groups (6 mg/kg NPC-21, 12 mg/kg NPC-21, or placebo) in a 4:1:4 ratio. Randomization will be stratified by region (United States or Japan). Randomization will take place prior to first study drug administration after confirming all criteria. Randomization procedures may occur on Day -1 or Day 1 prior to first study drug administration.

2.2.3 Study Drug

[REDACTED]
Normal saline supplied by [REDACTED] will be used as the placebo.

2.2.4 Sample Size Determination

A total sample size of approximately 108 patients is planned for the study, with a 1:1 randomization ratio for 6 mg/kg NPC-21 versus placebo and another 12 patients for high-level dose of 12 mg/kg NPC-21 (4:1:4 randomization ratio for 6 mg/kg NPC-21, 12 mg/kg NPC-21, or placebo). The sample size calculation is based on the modified Intent-to-Treat (mITT) Population from the first dose of NPC-21 through Week 16 for the occurrence of CMV disease (CMV syndrome or tissue-invasive CMV disease) or CMV viremia (defined as the detection of ≥ 250 IU/mL in plasma measured by PCR analysis in central laboratory or meets the local criteria for CMV viremia measured by PCR analysis or antigenemia testing) primary endpoint. Assuming an early discontinuation rate of 15%, approximately 48 patients each in the 6 mg/kg NPC-21 and placebo arms are needed with a 2-sided significance level of 0.05 and a power of 80% to detect a difference between NPC-21 at a predicted incidence rate of CMV disease (CMV syndrome or tissue-invasive CMV disease) or CMV viremia of 30% versus 60% for placebo. In addition, a sample size of 12 patients for the 12 mg/kg NPC-21 arm is considered adequate for the planned exposure-response analysis.

2.3 Study Endpoints

2.3.1 Primary Efficacy Endpoint

The primary efficacy endpoint is the incidence of CMV disease (CMV syndrome [see Appendix C of protocol for definition of CMV syndrome] or tissue-invasive CMV disease [see Appendix D of protocol for definitions of CMV disease]) or CMV viremia (defined as the detection of ≥ 250 IU/mL in plasma measured by PCR analysis in central laboratory or meets the local criteria for CMV viremia measured by PCR analysis or antigenemia testing) by Week 16.

2.3.2 Secondary Efficacy Endpoints

The secondary efficacy endpoints include the following:

- Incidence of CMV disease or CMV viremia by Week 28
- Incidence of CMV disease
- Incidence of CMV viremia

- Time to detectable CMV disease or CMV viremia
- Time to detectable CMV disease
- Time to detectable CMV viremia
- Amount of CMV DNA by PCR analyzed by the central laboratory
- Incidence and duration of anti-CMV therapy during the Rescue Phase
- Changes in EQ-5D-5L score from Baseline to Weeks 16 and 28

2.3.3 *EuroQol 5 Dimensions 5 Levels Questionnaire*

EQ-5D-5L is developed by EuroQol Research Foundation and is a measure of health-related quality of life. It consists of two elements, 5-item questionnaire and EQ-Visual Analogue Scale. EQ-5D-5L is a version that further improves sensitivity of EQ-5D-3L and that provides respondents with a wider range of options to describe their health, which has five response levels.

- 5-Item Questionnaire: The questionnaire provides a simple descriptive profile of health state. The questionnaire comprises 5 dimensions (mobility, self-care, usual activities, pain/discomfort, anxiety/depression) and each dimension has 5 response levels (1-no problems, 2-slight problems, 3-moderate problems, 4-severe problems, 5-unable to/extreme problems).

2.3.4 *Safety Endpoints*

The safety of NPC-21 in CMV seronegative patients will be evaluated through physical examination findings, 12-lead ECGs, vital signs, changes in clinical laboratory assessments (blood biochemistry [including liver function tests and enzymes], hematology [including complete blood count with differential], coagulation, and urinalysis), and AE monitoring.

Events of serious hypersensitivity that are Grade 3 or higher or lead to treatment discontinuation will be monitored as AEs of special interest (AESIs) during this study. During the course of the study, vacuolization associated with immunoglobulin will be added as AESIs, and additional AESIs may be identified by the Sponsor.

3 STATISTICAL METHODOLOGY

3.1 General Considerations

3.1.1 *Analysis Day*

Analysis day will be calculated from the date of first dose of study drug. The day of the first dose of study drug will be Day 1, and the day immediately before Day 1 will be Day -1. There will be no Day 0.

3.1.2 *Analysis Visits*

The low analysis day of the analysis window will be calculated as the midpoint between the scheduled assessment and previously scheduled assessment for that parameter. The high analysis day of the analysis window will be calculated as the midpoint between the scheduled assessment and the next scheduled assessment for that parameter. Within each analysis visit, scheduled visits will be assigned to the analysis visit. If a scheduled visit is not available, unscheduled and early termination visits will be assigned to analysis visits using analysis visit windows based on the actual date the assessment took place.

Where multiple measurements for a particular parameter appear within an analysis window, the scheduled visit will be used. If no scheduled visit appears in the analysis window, the result closest to the target day will be used. If equidistant and both are unscheduled and/or early termination visits, the later result will be used for the summary measure. Specially, if patients do not receive the study drug at scheduled visit (e.g.,

Day 29) but receive the study drug within this visit window and record as “Unscheduled”, the results close to this unscheduled visit will be used if there are both results for scheduled visit and unscheduled visit. The analysis visit table below is applicable for both safety and efficacy analysis.

Analysis Visit	Target Day	Low Analysis Day	High Analysis Day
Baseline	1	Null	1
Day 8	8	2	11
Day 15	15	12	18
Day 22	22	19	25
Day 29	29	26	32
Day 36	36	33	39
Day 43	43	40	46
Day 50	50	47	53
Day 57	57	54	60
Day 64	64	61	67
Day 71	71	68	74
Day 78	78	75	81
Day 85	85	82	88
Day 92	92	89	95
Day 99	99	96	102
Day 106	106	103	109
Day 113	113	110	116
Day 120	120	117	123
Day 127	127	124	130
Day 134	134	131	137
Day 141	141	138	144
Day 148	148	145	151
Day 155	155	152	158
Day 162	162	159	165
Day 169	169	166	176
Day 183	183	177	189
Day 197/ET	197	190	200

3.1.3 Definition of Baseline

Baseline is defined as the last non-missing measurement prior to the first dose of study drug. Both date and time will be considered in baseline derivation. Measurement from Day 1 prior to study drug administration will be used. If not available, the last non-missing measurement prior to Day 1 will be used.

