4 SELECTION AND WITHDRAWAL OF PATIENTS

4.1 Inclusion Criteria

Patients who meet all of the following criteria will be eligible to participate in the study:

1. Male or female patients 18 to ≤ 75 (<76) years of age in the United States or 20 to ≤ 75 (<76) years of age in Japan at the time of obtaining informed consent.
2. Patients must be CMV seronegative pre-transplant and scheduled to receive or have received (within 7 days prior to first study drug administration) a first kidney transplant from a CMV seropositive donor.
3. Patients must be willing and able to give written informed consent for participation in the study.
4. Patients must be eligible to undergo kidney transplantation from a living or deceased donor, as per institutional standards.
5. Female patients of non-childbearing potential must be either surgically sterile (hysterectomy, bilateral tubal ligation, salpingectomy, and/or bilateral oophorectomy at least 26 weeks before Screening) or postmenopausal, defined as spontaneous amenorrhea for at least 2 years, with follicle-stimulating hormone (FSH) in the postmenopausal range at Screening, based on the laboratory's reference range.
6. Female patients of childbearing potential (ie, not postmenopausal or surgically sterilized) must have a negative urine or serum pregnancy test result at Screening. Participating female patients of childbearing potential must agree to use 1 of the following throughout the duration of the study and for 90 days following the last study drug administration:
 - One highly effective method of contraception and an acceptable barrier method (condom used by male partner plus spermicide).
 - Two highly effective methods of contraception.

Investigators will select the appropriate methods of contraception in accordance with local regulatory requirements. Highly effective methods of contraception that result in a low failure rate (ie, $<1\%$ per year) when used consistently and correctly include the following:

- Combined (estrogen and progestogen containing) hormonal contraception associated with inhibition of ovulation (oral, intravaginal, or transdermal), progestogen-only hormonal contraception associated with inhibition of ovulation (oral, injectable, or implantable), intrauterine device, or intrauterine hormone-releasing system for at least 12 weeks before Screening.
- Bilateral tubal occlusion or vasectomized partner at least 26 weeks before Screening.

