6.2 Screening Visit (Day -14 to Day -1)

The following procedures will be performed at the Screening Visit:

- Obtain informed consent.
- Perform pre-Randomization (see Section 6.3 for details).
- Obtain demographics.
- Obtain medical/surgical history and present illness.
- Record prior and concomitant medications.
- Obtain height.
- Obtain body weight (prior to pre-Randomization).

Note: In case of hemodialysis patients, body weight is defined immediately after dialysis or dry weight. In case of peritoneal dialysis patients, body weight is defined after removal of dialysate or dry weight.

Note: Body weight measured within 7 days prior to pre-Randomization is permitted.

- Perform complete physical examination.
- Record vital signs (systolic and diastolic blood pressure, pulse rate, and body temperature).
- Perform urine or serum pregnancy test for females of childbearing potential only.
- Perform FSH test for females of non-childbearing potential only (if necessary).
- Collect blood sample for CMV serology for analysis by the local laboratory (within 90 days of Randomization).
- Collect blood samples for blood biochemistry, hematology, and coagulation for analysis by the local laboratory.
- Collect urine sample for urinalysis by the local laboratory (if possible).
- Collect blood samples for CMV DNA analysis or CMV antigenemia testing for analysis by the local laboratory.
- Perform 12-lead ECG.
- Confirm patient meets all inclusion criteria and no exclusion criteria (until Randomization).
- Perform Randomization if Randomization will occur on Day -1 (see Section 6.3 for details).
- Record adverse events.

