- a. Screening procedures will take place up to 14 days prior to first study drug administration.
- b. The Treatment Period will begin as soon as practical post-transplant but no later than 7 days post-transplant.
- c. During the Treatment Period, visits on dosing days (Day 1 and at Weeks 4, 8, and 12) should be conducted in person. Visits on non-dosing days of the Treatment Period (Weeks 1, 2, 3, 5, 6, 7, 9, 10, 11, 13, 14, 15, and 16) may be conducted by home healthcare services (United States only). Home healthcare services may perform the following procedures at non-dosing day visits: record concomitant medications, obtain body weight, perform physical examination, record vital signs, collect samples for analysis by the central laboratory, perform 12-lead ECG, perform EQ-5D-5L, and record adverse events.
- d. After first study drug administration, patients who develop detectable CMV disease (CMV syndrome or tissue-invasive CMV disease) or CMV viremia (defined as the detection of ≥250 IU/mL in plasma measured by PCR analysis in central laboratory or meets the local criteria for CMV viremia measured by PCR analysis or antigenemia

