3.3.4 Demographic and Baseline Characteristics

The following demographic and baseline characteristics will be summarized:

- Country (United States, Japan)

- Age (Years)
- Age group (< 65, ≥ 65)
- Sex (Male, Female)
 - Childbearing potential
- Ethnicity (Hispanic or Latino, Not Hispanic or Latino, Not Reported, Unknown)
- Race (American Indian or Alaska Native, Asian, Black or African American, Native Hawaiian or Other Pacific Islander, White, Other: Specify)
- Height (cm)
- Weight at pre-randomization (kg)
- Weight group (< 100 kg, ≥ 100 kg)
- Body mass index (kg/m²)
- Time from transplantation to first dose date(days)
 - Day = First dose date of study drug – date of kidney transplant + 1.
- Primary disease (Diabetic Kidney Disease, Glomerulonephritis, Polycystic Kidney Disease, Other, Not Specified, Unknown)
- Donor status (Deceased, Living)
- ABO compatibility (Compatible, Incompatible)
- Dialysis introduction (Yes, No)
 - Dialysis specify (Hemodialysis, Peritoneal Dialysis)
- Central CMV DNA level (IU/mL) at baseline
- Induction therapy (Yes, No), if yes, summarize by the below categories:
 - Alemtuzumab
 - ATG (Thymoglobulin®)
 - Rituximab
 - Basiliximab
 - Bortezomib
 - Eculizumab
- Immunosuppressive agents at randomization (Azathioprine, Belatacept, Cyclosporine, Everolimus, Gusperimus, MMF, Sirolimus, Steroids, Tacrolimus)

Demographic and baseline characteristics will be summarized with descriptive statistics or counts and percentages of patients as appropriate by treatment group and in total for all defined analysis populations.

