3.7.2 Clinical Laboratory Evaluations

Standard clinical laboratory profiles for blood biochemistry, hematology, coagulation, and urinalysis will be evaluated at the local laboratory at Screening and at the local laboratory (Japan sites) and central laboratory (US sites) prior to study drug administration on dosing days (Day 1 and at Weeks 4, 8, and 12) and at Weeks 1, 2, 6, 10, 14, 16, 20, 24, and 28. Samples for evaluation by the central laboratory may be collected by home healthcare services at non-dosing day visits. See Appendix B of the protocol for a complete list of laboratory analytes.

Clinical laboratory evaluations will be summarized using descriptive statistics if sufficient data is available for selected laboratory parameters including absolute measurements and changes from baseline by scheduled time of evaluation. Changes from baseline by scheduled time of evaluation will include last analysis visit, maximum post-treatment value, and minimum post-treatment value. Both scheduled and unscheduled post-treatment visits will be considered for the summaries of the maximum and minimum post-treatment values.

Abnormal laboratory results will be graded according to NCI CTCAE v5.0. A shift table, presenting the 2-way frequency tabulation for baseline and the worst post-baseline grade according to NCI CTCAE grades, will be provided for selected clinical laboratory tests. For select parameters (e.g. glucose), separate shift tables indicating hyper-and hypo-directionality of change may be produced. The worst post-baseline grade will be derived from all post-baseline visits including scheduled and unscheduled.

The shift table for all parameters will be provided based on the categories Low, Normal and High based on normal ranges. Hyper-and hypo-directionality of change may be produced.

Clinical laboratory evaluations will be listed by-patient. Abnormal values will be flagged.

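### If a patient's Day 1 kidney-function result is missing, the SAP's baseline rule can put a pre-transplant value in its place, and change and shift tables could then show declining graft function as stable or improved

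*SAP*

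**What the plan says.** SAP 3.1.3 defines baseline as the last non-missing pre-dose measurement. It gives priority to the first-dose day: "Measurement from Day 1 prior to study drug administration will be used". If that value is absent, "If not available, the last non-missing measurement prior to Day 1 will be used". The analysis-visit table in SAP 3.1.2 gives Baseline no lower day limit. Neither section mentions the transplant.

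The protocol fixes what can lie before Day 1. Appendix A, footnote a: "Screening procedures will take place up to 14 days prior to first study drug administration". Footnote b: "The Treatment Period will begin as soon as practical post-transplant but no later than 7 days post-transplant". Inclusion criterion 2 admits patients "scheduled to receive or have received (within 7 days prior to first study drug administration) a first kidney transplant", and Appendix A places transplantation in the Screening column. The Screening weight note in Protocol 6.2 provides for dialysis patients: "In case of hemodialysis patients, body weight is defined immediately after dialysis or dry weight".

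Under SAP 3.7.2, baseline feeds changes from baseline (including those for the last visit and the maximum and minimum post-treatment values), a "2-way frequency tabulation for baseline and the worst post-baseline grade according to NCI CTCAE grades", and a Low/Normal/High shift table. Protocol Appendix B lists creatinine, blood urea nitrogen and eGFR in the chemistry panel.

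**The concern.** A baseline should describe the patient's state just before study drug. For creatinine, blood urea nitrogen and eGFR, that means the function of the transplanted kidney. A value drawn before transplant describes the native kidneys, often in a patient on dialysis, yet the rule accepts it if nothing later is on file.

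For these three tests the error is likely to run one way. A pre-transplant creatinine or urea is likely to be higher, and an eGFR lower, than the missing Day 1 value. A decline in graft function after dosing could then appear as no change or as improvement in the change and shift tables. Safety is part of the primary objective, and changes in laboratory assessments are among the listed safety endpoints (SAP 2.3.4). The SAP plans no flag, count or sensitivity analysis for fallback baselines.

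There is a second, smaller issue at US sites. Screening samples go to the local laboratory and later ones to the central laboratory, so a fallback baseline also compares two laboratories.

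**Working it through.** The plan states no figure on this point: it gives neither a rate of missing Day 1 results nor any creatinine values. The planned sizes (108 in total, 48 in each main arm) serve only as denominators.

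**Step 1. Which Screening days are pre-transplant?** Screening runs from Day -14 to Day -1, and SAP 3.1.1 has no Day 0. First dose is at most 7 days after transplant, so the earliest transplant day is Day -7. Hence:
- A sample from Day -14 to Day -8 (7 of the 14 Screening days) must be pre-transplant.
- A sample from Day -7 to Day -1 may fall on either side of the transplant.

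**Step 2. When is the rule triggered?** All three conditions must hold for a given test:
1. the Day 1 pre-dose result is missing;
2. the Screening sample preceded the transplant;
3. no unscheduled post-transplant, pre-dose value exists.

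**Step 3. What happens to the change score?** Reported change = worst on-study value - Screening value. Intended change = worst on-study value - Day 1 value. The error is therefore Day 1 value - Screening value. The creatinine values below are assumptions: Day 1 1.5 mg/dL, worst on-study 3.0 mg/dL.

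| Screening (assumed, mg/dL) | Reported change | Intended change |
|---|---|---|
| 4 | 3.0 - 4 = -1.0 | 3.0 - 1.5 = +1.5 |
| 6 | 3.0 - 6 = -3.0 | +1.5 |
| 8 | 3.0 - 8 = -5.0 | +1.5 |
| 10 | 3.0 - 10 = -7.0 | +1.5 |

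The rise disappears whenever the Screening value is at or above the worst on-study value, and is understated whenever Screening lies between the Day 1 and worst values. In the shift table, on any scale where the grade does not fall as creatinine rises, a baseline of 4 or more cannot have a lower grade than a worst value of 3.0. The cell then shows no worsening.

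**Step 4. How many patients, and how far could an arm mean move?** Let m be the share with a missing Day 1 result, f the share of those whose fallback is pre-transplant, and g the gap between Screening and Day 1. All are assumed; g runs from 4 - 1.5 = 2.5 to 8 - 1.5 = 6.5 mg/dL. Patients affected = N × m × f. Shift in arm mean change = -m × f × g.

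| m | f | of 108 | of 48 | shift in mean (mg/dL), g = 2.5 to 6.5 |
|---|---|---|---|---|
| 2% | 50% | 1.1 | 0.5 | -0.025 to -0.065 |
| 5% | 50% | 2.7 | 1.2 | -0.06 to -0.16 |
| 5% | 100% | 5.4 | 2.4 | -0.125 to -0.325 |
| 20% | 100% | 21.6 | 9.6 | -0.50 to -1.30 |

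The last row is an outer bound, not an expectation.

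**The case against.** The strongest reply is that this is an edge case. The Day 1 blood sample is a required procedure (Protocol 6.4.1) at a visit that should be in person; only urine is collected if possible, and that qualifier also applies at Screening. The rule takes the last non-missing value, not Screening as such, so an unscheduled post-transplant result would be used. Some patients are screened after transplant, and dialysis is recorded as yes or no, so not every patient need be on it. All of this stands. It limits the frequency but does not make the rule right when it is triggered.

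Deterioration also remains visible elsewhere. SAP 3.7.2 summarizes absolute values, flags abnormal results in listings and tabulates the worst post-baseline grade from all visits. Protocol 9.1 has clinically significant abnormalities reported as adverse events, and the DSMB reviews unblinded individual data. Safety is descriptive and the rule is the same in every arm. This also stands, so a reader who inferred that harm to the graft would go undetected would be going beyond the documents.

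A reader might also infer that the rule hides deterioration in blood tests generally. The documents do not support that. For hematology a pre-transplant value could hide or exaggerate a fall, depending on which side of the missing Day 1 value it lies. Nor is there a case for body weight, for which the SAP plans no change analysis. The vital-sign flags in SAP 3.7.3 do use baseline, but nothing in the documents shows that a pre-transplant reading is invalid for them.

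Finally, a Day 1 value taken very soon after surgery may not reflect settled graft function either. That is true, and a date condition does not cure it. It is a limit of dosing in the first week, not a reason to accept a baseline from another kidney.

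**Conclusion.** The point holds as a minor one. SAP 3.1.3 permits a pre-transplant value as baseline. For creatinine, blood urea nitrogen and eGFR, the change-from-baseline and shift outputs of an affected patient could then show a decline as stable or improved. Absolute values, listings, adverse events, efficacy results and the sample size are untouched.

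That the rule allows this, and that any Screening sample from Day -14 to Day -8 precedes the transplant, follows from the text alone. The size does not: missing rates, the share of pre-transplant fallbacks and creatinine levels are all assumptions. Because the Day 1 sample is required, the number affected is probably small and may be zero.

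**What to change.** - **Kidney-function tests (creatinine, blood urea nitrogen, eGFR).** Add to SAP 3.1.3 that a fallback baseline must be dated after the kidney transplant and before the first dose. Otherwise baseline is missing for change and shift outputs, and the on-study values are kept. A sample from the day of transplant should count as pre-transplant unless its time shows otherwise.
- **Other laboratory tests.** Keep the current fallback, since removing it would discard usable baselines. Flag pre-transplant baselines, report their number by arm, and repeat the shift tables without them.
- **US sites.** Also flag any fallback baseline that comes from the local laboratory; the date condition alone does not deal with this.
- **Body weight and vital signs.** No change.

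The cost is one date condition, a flag and a count, plus a few missing baselines in the kidney-function tables. The transplant date is already used to derive time from transplantation to first dose (SAP 3.3.4). The database was locked on 30 March 2023 and an addendum followed on 15 May 2023, so the change belongs in a further addendum or in the Clinical Study Report, labelled as made after lock. If no patient had a pre-transplant fallback baseline, one sentence in the report closes the matter.
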